7.5 Study Outcomes

Primary:

- i) *Difference in the mortality rate in the first month following gastrostomy in PEG and PIG/RIG patients.*

Secondary:

- i) *Difference in the complication rate (classified in groups according to seriousness and time of occurrence) following gastrostomy in PEG and PIG/RIG patients.*
- ii) *Median survival time from (a) placement of feeding tube, (b) symptom onset, and (c) time of diagnosis of the disease in PEG and PIG/RIG patients.*
- iii) *Nutritional status changes (weight and BMI) following gastrostomy in PEG and PIG/RIG patients.*
- iv) *Self-perceived quality of life changes (measured by MQOL, gastrostomy questionnaire and qualitative interviews) following gastrostomy in PEG and PIG/RIG patients.*
- v) *Change in carer quality of life as measured by MCSI and qualitative interviews.*

Analysis will also include looking into how factors, such as (a) respiratory status, (b) site of symptoms onset, and (c) stage of disease, influence safety and survival following gastrostomy in PEG and PIG/RIG patients.

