This form will be completed at the end of the gastrostomy procedure, either by the local champion or the member of the team performing the gastrostomy insertion. The form is designed to capture the details of the procedure with regard to staffing; gastrostomy equipment; drugs given; patient monitoring and respiratory support; as well as, any complications that occur during the procedure.

iv) 3-month Follow Up Patient Evaluation Form (see Appendix 4)

This form is designed to capture data with regard to gastrostomy complications occurred prior to patient's hospital discharge and those occurred after the hospital discharge up to the 3-month patient evaluation. Weight and ALSFRS-R for each patient will also be recorded. This form will be completed by the local champion after a patient's usual follow up visit which coincides nearest with 3 months post gastrostomy.

v) 12-month Follow Up Patient Evaluation Form (see Appendix 5)

This form is designed to capture data with regard to gastrostomy complications occurred in the period of time between the 3-month patient evaluation and the 12-month patient evaluation. Weight and ALSFRS-R for each patient will also be recorded. This form will be completed by the local champion after a patient's usual follow up visit which coincides nearest with 12 months post gastrostomy.

vi) McGill Quality of Life Questionnaire (MQOL) (see Appendix 7)

This is a well-established questionnaire, designed in the context of palliative care, to identify the health-related quality of life of patients with a terminal illness. It balances physical and non-physical aspects of quality of life, and includes both positive and negative influences on quality of life [53]. This questionnaire will be completed by patients at baseline and at 3 months post gastrostomy.

vii) Modified Caregiver Strain Index (MCSI) (see Appendix 8)

This is a well-established questionnaire, designed to identify the strain levels among informal carers of patients with long-term illness. It will be used in this study to assess the quality of life of the main carer of the patient and the impact that the treatment is having on the carer [54]. It will be completed by carers at baseline and at 3 months post gastrostomy.

viii) Gastrostomy-specific questionnaire (Gastro-Qu) (see Appendix 9)

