7.7 Data Analysis

Quantitative data analysis

All quantitative data will be managed and analysed using SPSS for Windows version 14.0 (SPSS Inc., 1998). Exploratory data analysis will be initially carried out to establish the distribution of all continuous and categorical variables. Descriptive statistics (means, standard deviations, percentages) will be used to describe the characteristics of the participating centres, the participants and all the main variables of the study. Non-parametric tests (Spearman rank correlation tests and Mann Whitney U tests) will be performed for non-normally distributed continuous variables. Cronbach's alpha (α) coefficients will be determined for the measures that will be used in the study (i.e., MQOL, MCSI, gastrostomy questionnaire) in order to establish their internal consistency.

Continuity corrected Chi-square (χ^2) tests will be performed to determine the difference in the first-month mortality rate and the complication rate following gastrostomy in PEG and PIG/RIG patients. The same tests will be also performed to determine the self-perceived quality of life changes following gastrostomy in PEG and PIG/RIG patients as well as to determine the changes in carer quality of life. Kaplan-Meier survival curves will be used to determine the median survival time from placement of feeding tube, symptom onset and time of diagnosis of the disease in PEG and PIG/RIG patients. Independent samples t-tests will be used to determine the nutritional status changes following gastrostomy in PEG and PIG/RIG patients. Predictors of survival (e.g., respiratory status, site of symptom onset, stage of disease) following gastrostomy will be determined using logistic regression analysis and Cox proportional hazards regressions analysis.

Qualitative data analysis

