Reduce carer burden		
Other _____		

Preferred Gastrostomy procedure for this patient: *(please tick)*

PEG PIG RIG Surgical
 Other _____

Why was this method selected for this patient? *(please, use the space provided)*

.....

Has the patient's perception of gastrostomy influenced the timing or any other aspect of dysphagia management? *(please tick)*

Yes No

▪ If yes, please detail how in the space provided:

.....

Important Note

Please issue the MQOL questionnaire to the patient and the MCSI to the carer. These must be completed by the participants before the gastrostomy placement.

Peri-Procedure Patient Evaluation

Coded participant number: _____

Date of hospital admittance: _____

Clinic: _____

Date of Procedure: _____

Type of Gastrostomy : _____

Staffing: *(please, tick if present)*

Anaesthetist Anaesthetic assistant Radiologist

Radiographer Endoscopist Nurse

Other _____

Patient pre procedure: O₂ sats _____ pCO₂ _____

Drugs given for gastrostomy:

Name	Amount	Indication
1		
2		
3		
4		
5		

Monitoring: *(please, tick those performed through procedure and record most abnormal value)*

Heart rate _____ BP _____ Respiratory Rate _____

O₂ Sats _____ CO₂ _____

Respiratory support: *(please tick)*

Does patient use NIV routinely? Yes No

Was NIV used during the gastrostomy? Yes No

Was supplementary oxygen given? Yes No

Gastrostomy equipment:

Tube product number/type _____

Tube size _____

Tube manufacturer _____

Complications:

Duration of procedure _____

Was this a difficult gastrostomy? *(please, tick)* Yes No

Indicate complications: *(please, tick any that apply)*

Desaturation Respiratory arrest Laryngeal spasm

Patient distress Failure to complete Haemorrhage

Please, detail other complications or notable issues relating to this gastrostomy procedure
(please, use the space provided):

.....

.....

.....

.....

.....

3 Month Follow Up Patient Evaluation

Coded participant number: _____

Date of evaluation: _____

Date of discharge after gastrostomy: _____

Weight (Kg): _____

Complications following Gastrostomy: *(please, tick any that apply for complications that have occurred since gastrostomy insertion)*

	Prior to Discharge	After Discharge
Tube blockage		
Tube displacement		
Tube leakage		

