Infection		
Granulation tissue		
Pain		
Gastric haemorrhage		
Perforation		
Peritonitis		
Pneumonia		
Increased anxiety		
Nausea		
Diarrhoea		
Constipation		
Fatigue		

Please, state how these complications were managed: *(please, use the space provided)*

.....

.....

.....

.....

.....

Repeat gastrostomy required: (please, tick) Yes No

If yes,

- Reason _____
- Method used for 2nd procedure _____

Bedside tube replacement required: (please, tick) Yes No

If yes,

- Reason _____

If patient dead:

- Date of Death _____
- Cause of Death _____
- Was cause of death directly related to Gastrostomy procedure? *(please tick)*
Yes No Uncertain

- If available record the value and date of the last post procedure weight:

Weight (Kg) _____ Date recorded _____

Please detail other complications or notable issues relating to this gastrostomy procedure:
(please, use the space provided)

.....
.....
.....
.....
.....
.....
.....

Important Note

Please issue the MQOL and Gastro-Qu questionnaires to the patient and the MCSI to the carer. These must be completed by the participants approximately at 3 months following gastrostomy.

12 Month Follow Up Patient Evaluation

Coded participant number: _____

Date of evaluation: _____

Weight (Kg): _____

Complications following Gastrostomy: *(please, tick any that apply for complications that have occurred since the 3 month follow up visit)*

- | | | | | | |
|---------------------|--------------------------|--------------------|--------------------------|--------------|--------------------------|
| Tube blockage |  | Tube displacement |  | Tube leakage |  |
| Infection |  | Granulation tissue |  | Pain |  |

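### The complication outcome is to be grouped by seriousness, but no study form records seriousness for any complication, so grouping can be by type only

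*Protocol*

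**What the plan says.** Section 7.5, secondary outcome (i), is the difference in complication rate between PEG and PIG/RIG patients, with complications "classified in groups according to seriousness and time of occurrence". Section 7.7 plans continuity-corrected chi-square tests to "determine the difference in the first-month mortality rate and the complication rate following gastrostomy in PEG and PIG/RIG patients".

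The data come from three forms described in section 7.2 and reproduced in the appendices:

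- The peri-procedure form (Appendix 3) covers "any complications that occur during the procedure".
- The 3-month form (Appendix 4) covers "gastrostomy complications occurred prior to patient's hospital discharge and those occurred after the hospital discharge up to the 3-month patient evaluation". Its instruction is to "tick any that apply for complications that have occurred since gastrostomy insertion", with one column for before discharge and one for after.
- The 12-month form (Appendix 5) covers "gastrostomy complications occurred in the period of time between the 3-month patient evaluation and the 12-month patient evaluation", with one tick per item.

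Both follow-up forms then ask, once for all ticked items together, "Please, state how these complications were managed".

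Section 4, aim (vi), hypothesises that the techniques differ in complications such as infection, respiratory complications, tube displacement and loss of the tube.

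**The concern.** The outcome has two classifying dimensions, and the forms supply only one of them. A bare tick for infection covers everything from a minor stoma-site problem to a life-threatening event. Suppose the same proportion of patients in each group has infection ticked. The chi-square result is then the same whether one method's infections were trivial and the other's severe, or the reverse. That is the distinction the seriousness grouping is meant to bring out.

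The study is not randomised and is meant to inform guidelines. If seriousness has to be worked out afterwards from unstructured text, the comparison depends on judgement made by someone who can usually tell which method was used.

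**Working it through.** No arithmetic in the plan bears on this point, so the check sets the outcome definition against the fields on the forms.

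**Seriousness, item by item**

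| Form | Complication items | Tick boxes | Seriousness code per item |
|---|---|---|---|
| Peri-procedure | 6 | 6 | none |
| 3-month | 15 | 15 × 2 columns = 30 | none |
| 12-month | 15 (the same list) | 15 | none |
| Total | | 6 + 30 + 15 = 51 | 0 |

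**Other information on seriousness on these forms**

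- Each follow-up form has one free-text management box for all complications. With several items ticked, the text need not map to any one of them.
- Each follow-up form asks about repeat gastrostomy and bedside tube replacement (yes/no with reason), the cause of death, and whether death was related to the procedure. These mark some extreme outcomes for the patient. They do not grade the ticked items.
- Each form has a further free-text box for other complications or notable issues.
- The peri-procedure form asks for the most abnormal monitoring values. That gives some measure of the depth of a desaturation, but nothing comparable for the follow-up items.

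**What grouping by type can and cannot do.** Some types sort themselves: perforation, peritonitis and respiratory arrest on one side, granulation tissue and constipation on the other. Infection, pneumonia, pain, tube displacement and haemorrhage each run from mild to severe, so their type does not settle their group. Three of these (infection, pneumonia, tube displacement) are the follow-up items closest to the hypothesis in section 4 (vi).

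**Whether later grading could be blind.** The participant code begins with the centre number (section 8.1). Section 7.6 says that most centres use only PEG or only PIG/RIG. As the forms stand, anyone grading from the coded copies can usually infer the method.

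**Time of occurrence.** The forms yield four successive groups: during the procedure, before discharge, discharge to the 3-month evaluation, and 3 to 12 months. The field "Date of Procedure" on the peri-procedure form anchors the start, and the discharge and evaluation dates are recorded too. This part of the outcome can be built. The windows do vary in length. Discharge differs by patient, and the follow-up forms are tied to the routine visit nearest to 3 or 12 months (section 7.1). Section 7.4 puts visits about every 2 to 3 months. If they are evenly spaced, the nearest visit can lie up to 2/2 = 1 month or 3/2 = 1.5 months either side of target.

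**The case against.** The strongest reply is that grouping by seriousness may simply mean assigning complication types to groups. That allocation commonly belongs in a statistical analysis plan, which is not at hand. This stands as far as it goes: the absence of a list of serious types from the protocol is not the finding. It does not answer the point about severity within a type. If that is not collected, an analysis plan cannot restore it.

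Three other sources could be offered:

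- **Gastro-Qu.** Patients rate pain, leakage, blockage, bleeding, infection and falling out from 1 to 4, so it would be wrong to say that severity is recorded nowhere. But the scale measures how much of a problem the patient found the tube. It is completed once, at 3 months, by patients able to return it, and has no pneumonia item.
- **Medical notes.** Section 8.2 names them as source data, with consent for local access. Grading from notes is possible, but no such step is described, and local staff know the method.
- **Patient-level items.** Repeat gastrostomy, tube replacement and related death are real information and should be used. They identify some serious courses without grading each complication.

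A reader might also infer more than the documents support:

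- **That the outcome cannot be built at all, because events have no dates.** Section 7.5 asks for time groups, not dates, and the forms supply four. The planned test on proportions needs no event dates.
- **That complications must be placed in the first 30 days.** The one-month window belongs to the mortality outcome. No such window is set for complications.
- **That the early/late split is biased because discharge timing differs between methods.** The documents give no length of stay by method or centre. This is a possibility that the recorded discharge dates would let the analysts examine.

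**Conclusion.** The point holds for seriousness and not for timing. None of the 6 peri-procedure items or the 15 items on each follow-up form records seriousness, so complications can be grouped by type only. Severity within infection, pneumonia and tube displacement cannot be compared reliably between PEG and PIG/RIG, nor graded blind to centre from the forms as they stand. Timing can be grouped as the outcome asks, in windows of varying length.

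The size is modest: one dimension of one secondary outcome, with no effect on the primary mortality comparison. It is a data-collection defect rather than missing detail, because the information may not be reliably recoverable later. The conclusion assumes that the appendix forms are those to be used and that no separate grading from the notes is planned elsewhere.

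**What to change.** Before recruitment:

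- Add a simple seriousness code beside each complication tick box on the peri-procedure, 3-month and 12-month forms. One illustration is: no treatment; bedside or community treatment; hospital admission or re-intervention; fatal. The levels are for the investigators to choose.
- State the resulting seriousness groups in section 7.5, so that they are fixed before any data are seen.
- Optionally, add an approximate date of first occurrence on the 3-month form, so that early events can be placed in days since the procedure.

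The code would still be entered by site staff who know the method, so it does not blind the grading. It replaces later judgement from shared free text with a fixed rule applied to each event when the form is completed.

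The cost is one form revision and slightly more form-filling for the local champion. Section 18 describes recruitment as still to begin, so the change is cheap at that stage.

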7.1 Plan of Investigation

A. Centre Pathway Review

We have 15 MND centres committed to participating in PROGAS. A provisional survey of the centres has identified that 360 gastrostomies are performed for MND patients in the UK per year. The first component of PROGAS will be to perform a detailed survey of current practice regarding gastrostomy pathways at each centre. A questionnaire will be completed by the director of each centre capturing data regarding indication for gastrostomy, timing, and type of gastrostomy. This survey will highlight current practice, good practice points and will enable refinement of the data analysis plan of the main phase of the study. The centre director will also identify a “local champion” who will assist in recruiting patients and liaise with the central study co-ordinator who will be based in Sheffield.

B. Prospective evaluation of Gastrostomy

Following ethical and research governance approvals, participants will be recruited into PROGAS from all participating sites over a period of 21 months. All centres will be encouraged to maintain their usual practice and protocols for gastrostomy provision.

i) Patient enrolment

The study will be discussed with patients and carers, when a gastrostomy is being considered by the clinical team as part of their normal standard care. Patients and carers will be asked to consent to the study at the time of referral for gastrostomy. We will aim to recruit 504 patients and carers over 21 months. This figure is based on 80% (i.e., the anticipated patient response rate) of the 630 eligible patients seen according to the provisional survey of centres undertaken.

ii) Pre Gastrostomy Patient Evaluation

Once patients are successfully recruited and consented into PROGAS, the local investigator will complete a Pre Gastrostomy Patient evaluation form. This form is designed to capture routine data already being recorded in clinics, including demographic and functional characteristics, nutritional and respiratory status and gastrostomy-related data.

iii) Peri-Procedure Evaluation

Patients will then undergo the gastrostomy procedure. At the end of the procedure, either the local investigator or a member of the team performing the gastrostomy insertion will complete a Peri-procedure evaluation form. This form will capture the details of the procedure as well as any complications that occur during the procedure.

iv) Follow Up Patient Evaluation

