7.2 Measures, Questionnaires and Interviews

A. Main Study

i) *Centre Pathway Review Form (see Appendix 1)*

This is an initial questionnaire which will be completed by the centre director at each site. It is designed to assess the current clinical practice of gastrostomy insertion in patients with MND at each centre. It will record data with regard to the number of gastrostomies performed; the type of gastrostomies offered and the preferred circumstances for each different type; as well as the decision-making criteria influencing the timing of gastrostomy.

ii) *Pre Gastrostomy Patient Evaluation Form (see Appendix 2)*

This evaluation form, which will be completed by the local champion at enrolment, is designed to capture data already being recorded in the neuromuscular clinic as part of routine clinical care. It will record the following data about a recruited patient:

Demographic and functional characteristics: Demographic and functional characteristics of the patients will be recorded including age, gender, date of onset of MND symptoms, date of MND diagnosis, site of onset of MND, severity of bulbar dysfunction, time since first symptom of significant weakness, weight, and height. A functional rating scale for MND/ALS, the Amyotrophic Lateral Sclerosis Functional Rating Scale – Revised (ALSFRS-R) [52] will also be completed (see Appendix 6). These data are available in each patient's medical records.

Measures of respiratory function: Forced vital capacity (FVC); Sniff Nasal Inspiratory Pressure (SNIP); and arterial blood gas or non-invasive measurement of P_{tO_2} - P_{tCO_2} , will be recorded. These parameters of respiratory function are measured routinely in the neuromuscular clinic as part of routine clinical care.

Indices of disease progression: Weight measurement and the ALSFRS-R score will be recorded for each patient. These parameters of disease progression are also measured routinely in the neuromuscular clinic as part of routinely clinical care.

Gastrostomy-related data: The pre-procedure evaluation form will also record data for each patient with regard to gastrostomy indication; type of gastrostomy preferred and preference reasons; potential benefits of gastrostomy; and, patient's influence on the timing of gastrostomy.

iii) Peri-procedure Patient Evaluation Form (see Appendix 3)

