7.4 Participants and Recruitment

Inclusion & Exclusion Criteria

Patients, and their carers, will be recruited locally at the participating centres. Patients with MND will be eligible when a decision has been made to refer the patient for a gastrostomy, regardless of indication.

Patient Inclusion Criteria:

- i) A diagnosis of definite, probable, laboratory supported or possible MND, as defined by the revised El-Escorial criteria
- ii) A decision has been taken to refer the patient for a gastrostomy

Patient Exclusion Criteria:

- i) Contradiction to gastrostomy
- ii) Patient declines gastrostomy

Carer Inclusion Criteria:

- i) Being the main carer of an MND patient who has been referred for a gastrostomy placement.

Carer Exclusion Criteria:

- i) Patient declines to participate in an interview (only for the qualitative component of PROGAS)

Participant Recruitment

Patients and their carers will be recruited at each of the participating sites. A typical site (Sheffield Care and Research Centre for Motor Neurone Disorders), serving a population of approximately 2.2million undertakes approximately 16 gastrostomies per year for patients with MND. With the inclusion of 18 sites, and anticipating an 80% participant response rate, we estimate that we will recruit at least 504 patients over a 21-month recruitment period.

Patients and carers will be informed of the study after a decision to refer for a gastrostomy has been made by a member of the research team. Patients and carers who are not interested will not be contacted again for this study. A patient information sheet, explaining the details of the study, will be given to interested patients meeting all the inclusion criteria and none of the exclusion criteria and a carer information sheet will be given to interested carers. They will be asked to contact the local researcher if they would like to participate in the study. One follow up call will be made by a member of the research team, to initially interested patients and carers who do not contact the local researcher, approximately two weeks following the invitation. Patients and carers who respond negatively to the follow up call will not be contacted again for this study. Patients and carers who contact the local researcher and those who respond positively to the follow up call will be asked to provide their consent for participation in the study.

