Once consented and successfully recruited into the study the participants will be further informed verbally about the next stages of PROGAS by the local researcher and undergo the gastrostomy procedure as scheduled. Data will be collected, by a member of the research team, before and following the gastrostomy procedure with the completion of the pre-procedure and the peri-procedure gastrostomy patient evaluation forms, respectively. Following hospital discharge, the participants will continue their standard visits (approximately every 2-3 months) to the neuromuscular clinic as part of routine clinical care.

For this study data will also be collected, by a member of the research team, 3 months and 1 year following gastrostomy.

During their participation into PROGAS, patients will be asked to complete a health-related quality of life questionnaire (MQOL) twice (at baseline and approximately at 3 months following gastrostomy), and a gastrostomy-specific questionnaire once (approximately at 3 months following gastrostomy). Participating carers will be asked to complete a quality of life questionnaire (MCSI) twice (at baseline and approximately 3 months following gastrostomy). Both patients and carers will be given freepost/pre-paid envelopes to return the questionnaires to the study's central co-ordinator.

The recruitment process of patients and carers for the qualitative component of PROGAS at Sheffield and Leeds MND Care and Research Centres will be similar to the process described above. Once consented and recruited, participants will be contacted by the local researcher by telephone (approximately 3 months following the gastrostomy procedure) to arrange with each one a date and time for a face-to-face interview at a place of each participant's choice. For this part of PROGAS, we will aim to recruit 10 patients and 10 carers. Quantitative data will be collected as described for the other sites. A detailed visual representation of the recruitment process is shown in the following chart (Chart 1).

[figure not shown]

Chart 1: Participant recruitment flow chart

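### Weight and BMI change after gastrostomy is measured from enrolment, not from tube insertion, so it includes any change while the patient waits

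*Protocol*

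**What the plan says.** - **Outcome.** Protocol Section 7.5, secondary outcome (iii): "Nutritional status changes (weight and BMI) following gastrostomy in PEG and PIG/RIG patients". It serves hypothesis v in Section 4, that gastrostomy feeding goes with better nutritional status.
- **Baseline.** Section 7.1: "Patients and carers will be asked to consent to the study at the time of referral for gastrostomy". Section 7.2 says of the Pre Gastrostomy form, which holds weight and height: "This evaluation form, which will be completed by the local champion at enrolment". Under Section 7.4, some patients are reached by a follow-up call "approximately two weeks following the invitation", so their consent and baseline come later.
- **Procedure.** Section 7.4 has consented patients "undergo the gastrostomy procedure as scheduled". No maximum interval from baseline is given.
- **Weights taken.** Table 1 (Section 7.3) ticks weight before gastrostomy and at 3 and 12 months, and shows a dash at the peri-procedure point for all centres. On the peri-procedure form, Section 7.2 says: "The form is designed to capture the details of the procedure with regard to staffing; gastrostomy equipment; drugs given; patient monitoring and respiratory support". The form itself (Appendix 3) has a line headed "Patient pre procedure" for oxygen saturation and pCO2, but no weight field.
- **Analysis.** Section 7.7 compares nutritional change between methods by independent samples t-tests and mentions no allowance for the wait.

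**The concern.** A change described as following gastrostomy should start when the tube goes in. Here it starts at a clinic evaluation some unknown time before. Section 6 describes ongoing weight loss in patients with severe dysphagia and presents tube feeding as a way to stabilise weight. The wait is thus the period in which loss is most expected, and it is counted as if it came after the tube.

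Two readings of the data are at stake. The first is the before-after change for hypothesis v, which would look worse than the change after insertion. The second is the comparison of methods. Section 7.6 says that most centres perform only one type of procedure, so a centre's waiting time goes with its method. A difference in waiting lists could then be taken for a difference between techniques.

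**Working it through.** The protocol states no sample size, standard deviation or expected effect for weight or BMI, so there is no figure to reproduce. The check has two parts.

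**1. What the schedule measures**

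Let W_e be the weight at enrolment, W_p the weight at the procedure and W_f the weight at follow-up.

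- Available from the scheduled visits: W_f − W_e.
- Named by the outcome: W_f − W_p.
- Identity: W_f − W_e = (W_f − W_p) + (W_p − W_e).

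The last bracket is the change during the wait. W_p is not recorded, so the bracket is not observed. BMI inherits the problem, because height is recorded once and BMI change is weight change divided by height squared.

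**2. How large it could be (assumed inputs only)**

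The protocol gives neither waiting times nor rates of loss. Assumptions: loss of 0.5, 1.0 or 1.5 kg/month, constant over the wait and equal in both methods; 4.345 weeks per month.

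*Before-after change.* Apparent loss = rate × wait in weeks / 4.345.
- 2-week wait: 0.5 × 2/4.345 = 0.23 kg, up to 1.5 × 2/4.345 = 0.69 kg.
- 6-week wait: 0.5 × 6/4.345 = 0.69 kg, up to 1.5 × 6/4.345 = 2.07 kg.

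Three months is 3 × 4.345 = 13.0 weeks. With a 6-week wait, 6/(6 + 13) = 32% of the interval from baseline to the 3-month weight lies before the tube.

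*Between methods.* Spurious difference = rate × difference in mean wait in weeks / 4.345. The false-positive rate is that of a two-sided 5% z-test with 200 analysed per group (assumed) and SD of change of 6 or 4 kg (assumed). The standard errors are 6 × √(2/200) = 0.60 kg and 4 × √(2/200) = 0.40 kg.

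| Difference in wait | Rate (kg/month) | Spurious difference (kg) | False-positive rate, SD 6 | False-positive rate, SD 4 |
|---|---|---|---|---|
| 0 weeks | any | 0 | 5% | 5% |
| 2 weeks | 0.5 | 0.23 | 6.7% | 8.9% |
| 2 weeks | 1.0 | 0.46 | 12% | 21% |
| 2 weeks | 1.5 | 0.69 | 21% | 41% |
| 4 weeks | 0.5 | 0.46 | 12% | 21% |
| 4 weeks | 1.0 | 0.92 | 33% | 63% |
| 4 weeks | 1.5 | 1.38 | 63% | 93% |

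Example: 0.46/0.60 = 0.77 standard errors, and Φ(0.77 − 1.96) + Φ(−0.77 − 1.96) is about 12%.

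The first row matters as much as the others. With equal waits and equal rates of loss, the comparison of methods is unbiased, although each group's own change still contains pre-tube loss.

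**The case against.** **The data to handle the wait are already collected.** This is the strongest counter-argument. The Pre Gastrostomy form records the evaluation date, the referral date, the current weight and an earlier dated weight. The Peri-Procedure form records the procedure date. A reader might infer that change after the tube cannot be derived at all. That goes too far: each patient's evaluation-to-procedure interval is known, and a prior rate of loss can be estimated when the two weights have different dates. What stands is that this is modelling, not measurement. It assumes a steady rate of loss and waits that overlap between methods, and Section 7.7 plans no such step.

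**The analysis detail may sit in an SAP.** The protocol does not spell out how change is computed, and Sections 7.6 and 7.1 foresee examining key variables and refining the analysis plan. This is fair as regards covariates. But an SAP cannot supply a weight that no form collects.

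**The wait is shorter than referral to procedure.** Correct. The form is "completed by the local champion at enrolment", after consent, and consent may come two weeks or more after the invitation. The interval that counts is evaluation to procedure.

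**Bias between methods is not shown.** Also correct. A reader might infer that the comparison is biased against the method with the longer wait. The protocol ties method to centre, but gives no waiting times and nothing to say that they differ by method.

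**Not every patient loses weight while waiting.** Eligibility does not depend on the indication, marked weight loss is one tick box among several, and Section 6 names the nasogastric tube as another route of feeding. The rates above therefore should not be applied to every patient.

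**It may need an extra weighing.** The study relies on routine data, and the protocol does not say that patients are weighed on admission. This is a cost of the remedy and does not remove the problem.

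**Conclusion.** The point holds as a limitation of the measurement schedule. Weight and BMI change, as collected, runs from enrolment and so includes any change before insertion. For the before-after reading, the shift is against gastrostomy wherever patients lose weight while waiting. For PEG versus PIG/RIG, bias is possible but not demonstrated: about 0.5 to 1.4 kg for a 4-week difference in wait at 0.5 to 1.5 kg/month, and none if waits and rates are equal. Every number here rests on assumed rates, waits, SDs and group sizes.

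The reach is limited to this secondary outcome and hypothesis v; first-month mortality is untouched. Nor would an admission weight turn hypothesis v into a test of gastrostomy's effect, since there is no untreated comparator. It would make the measured change start at the right time. The change is worth making because it is cheap and cannot be made good once patients have passed through.

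**What to change.** 1. Add a weight on admission, with its date, to the Peri-Procedure form, and tick weight at the peri-procedure point in Table 1.
2. State in Sections 7.5 and 7.7 that weight and BMI change are measured from the admission weight, with BMI computed from the height already recorded. Keep the enrolment weight as a covariate, which means a linear model with a term for method in place of the plain t-test.
3. Where the admission weight is missing, use the enrolment weight and adjust for the evaluation-to-procedure interval from the dates on the two forms.
4. As a sensitivity analysis, repeat the comparison in all patients from the enrolment weight with that interval as a covariate. Missing admission weights may cluster by centre, and hence by method, so the mixed baseline in step 3 could otherwise bring back part of the bias.
5. Report the evaluation-to-procedure interval by method, so that readers can see whether the waits differed.

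**Cost.** One dated field on a form already completed for each procedure, one line in Table 1, and a few sentences in Sections 7.5 and 7.7. Some patients may not be weighed on admission, and ward scales may differ from clinic scales.
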